7.4 Categorical Variables

The categorical variables used in this study are shown below (Table 10).

Table 10: Categorical Variables Definitions

Variable	Categories
BMI (kg/m ²)	Underweight: < 18.5
	Normal range: ≥ 18.5 and < 25.0
	Overweight: ≥ 25.0 and < 30.0
	Obese: ≥ 30.0
FTND total score	Mild: 0 – 3
	Moderate: 4 – 6
	Severe: 7 – 10
ISO tar yields	1 – 5 mg
	6 – 8 mg

**Table 10: Categorical Variables Definitions**

Variable	Categories
	8– 10 mg > 10 mg
Nicotine level	<= 0.6 mg > 0.6 to <= 1 mg
Daily CC consumption over the last 4 weeks as reported at Screening (per day).	10-19 >19
CO breath test level (ppm)	≤ 10 > 10
COHb level	≤ 2% > 2%
Adverse event severity	Mild Moderate Severe
Adverse event relationship	Related Not related
Adverse event expectedness	No Yes
Action taken with study product due to adverse event	Product use interrupted Product use withdrawn Product use reduced None
Outcome of adverse event	Fatal Not recovered or not resolved Recovered or resolved Recovered or resolved with sequelae Recovering or resolving Unknown
Seriousness Criteria	Fatal Life-threatening Requires hospitalization Results in disability/incapacity Congenital anomaly/birth defect Other medically important event

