Data and information contained in this document are considered to constitute trade secrets and confidential commercial information, and the legal protections provided to such trade secrets and confidential information are hereby claimed under the provisions of applicable law. No part of this document may be publicly disclosed without the written consent of Philip Morris Products S.A.

Investigational Products; Dose; and Mode of Administration:

- Carbon Heated Tobacco Product 1.0 (CHTP 1.0). CHTP 1.0 will be provided by the Sponsor.
- Subject's own preferred commercially available non-menthol single brand of CC.

Duration of Study:

The entire study duration per subject will be 17 to 61 days including a Screening Period of up to 42 days prior to Admission on Day -3, a 9-day confinement period (from Day -3 to Discharge on Day 6) followed by the 7 days for the Safety Follow-up Period (until Day 13) plus up to 3 days.

Statistical Methods:

Analysis of BoExp will be conducted on the natural log scale. The transformed Day 5 data will be analyzed by means of a generalized linear model using randomized arm as covariate adjusting for the following baseline information: sex, average cigarette consumption over the previous 4 weeks (value at admission for stratification), and baseline value of the BoExp. Estimates of differences between groups will be back-transformed to provide relative effects. Assumptions of the analysis of variance (ANOVA) model will be tested. Markedly non-log normally distributed BoExp data will be transformed or analyzed by appropriate non-parametric methods.

Unless stated otherwise, all statistical tests will be two-sided and conducted at the 5% level, and all quoted confidence intervals (CIs) will be two-sided 95% confidence intervals.

Sample Size:

A total of 80 subjects (~ 40 in the CHTP 1.0 arm, ~ 40 in the CC arm) will be randomized. This sample size is needed to attain 80% power to detect a 50% reduction or more in the levels of MHBMA, 3-HPMA, S-PMA, and COHb in the CHTP 1.0 arm compared to the CC arm after 5 days of exposure, one sided test with 2.5% type I error probability.

The overall type I error will be protected by using a closed testing procedure (*i.e.*, testing the four above listed endpoints simultaneously).

Confidentiality Statement

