6.4 Method for Assigning Subjects to Study Arms

When all the eligibility criteria have been met, randomization will be done through the interactive web and voice response system (IxRS) on Day -1 at any time during the day. Subjects will be informed of their randomized study arm in the morning of Day 1, prior to 06:30 AM (the start of the Exposure Period). Subjects will be randomized to one of the 2 study arms: CHTP 1.0:CC in a 1:1 ratio.

Stratified randomization will be conducted by sex and by average daily CC consumption over the last 6 weeks prior to Admission as self-reported (smokers smoking 10 to 19 CC/day and smokers smoking > 19 CC/day). In each arm, each sex and each of the smoking strata should have a quota applied to ensure they represent at least 40% of the population.

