7.3.2 Identification of the Current Cigarette Brand

Identification of the current non-menthol CC brand smoked by the subject will be done at the Screening Visit and at Admission. Subjects will be asked to bring their own supply of current CC brand to the site and will have to hand their CC supply for the confinement period to the site collaborators. The site staff will document the brand name and yields in the source documentation.

7.3.3 Questions on Smoking History/Habits and Intention to Quit Smoking.

Subjects will be asked by the site collaborators the following questions about their smoking history and habits:

1. Have you smoked for at least the past 3 years? (yes/no)
2. How many years have you smoked? (numeric response, 2 digits)
3. On average, how many cigarettes per day have you smoked over the last 6 weeks? (numeric response, 2 digits)
4. On average, how many cigarettes per day have you smoked since you started smoking? (numeric response, 2 digits)
5. Have you used nicotine-containing products other than commercially available non-menthol CC within 6 weeks prior to admission? For example, any tobacco-based products or NRT, electronic cigarettes, or similar devices. (NOTE: This question is to be asked on the Admission Day only.)
6. On average, how would you describe your e-cigarette use over the last year? (check one)
 - a. Daily.
 - i. How much use per day? (numeric response, 2 digits)
 - b. Weekly.
 - i. How much use per week? (numeric response, 2 digits)
 - c. Sporadically. (less than once per week)
 - d. Tried e-cigarettes. (between 1 – 10 uses)
 - e. Never tried e-cigarettes.

Confidentiality Statement

Data and information contained in this document are considered to constitute trade secrets and confidential commercial information, and the legal protections provided to such trade secrets and confidential information are hereby claimed under the provisions of applicable law. No part of this document may be publicly disclosed without the written consent of Philip Morris Products S.A.

7. Are you planning to quit smoking during the next 3 months? (yes/no)

This self-reported CC daily consumption will be used to assess eligibility at the Screening Visit or on the Admission Day.

See [Appendix A](#) for the timepoints of assessment.

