12.4.4 Confirmatory Analyses

The hypothesis to be tested for each of the biomarkers of exposure of the primary and secondary objectives is that the geometric mean level on Day 5 of the biomarker for CHTP 1.0 is lower relative to CC.

Analysis of BoExp will be conducted on the natural log scale. In order to test the following hypothesis:

- Null hypothesis (H_0): $m_1 \geq m_2$
- Alternative hypothesis (H_1): $m_1 < m_2$

Where m_1 and m_2 are the geometric means of the biomarker levels on Day 5 for CHTP 1.0 and CC respectively.

The transformed data will be analyzed by means of a generalized linear model using product arm as covariate adjusting for the following baseline information: gender, average cigarette consumption over the previous 4 weeks, and baseline value of endpoint. Estimates of differences between groups will be back-transformed to provide relative effects.

Assumptions of the analysis of variance model will be tested. Markedly non-lognormally distributed BoExp data will be transformed or analyzed by appropriate non-parametric methods.

Should more than 20% of the subjects be excluded from the FAS, would the above confirmatory analysis will be repeated on the PP population.

Confidentiality Statement

Data and information contained in this document are considered to constitute trade secrets and confidential commercial information, and the legal protections provided to such trade secrets and confidential information are hereby claimed under the provisions of applicable law. No part of this document may be publicly disclosed without the written consent of Philip Morris Products S.A.

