12.1.1 Stratified Presentation

For the analysis and descriptive statistics of the primary study endpoints, the following stratification criteria will be used:

1. Sex (male; female).
2. Average daily CC consumption over the 6 weeks prior to admission as reported on the Admission Day (smokers smoking 10 to 19 CC/day and smokers smoking > 19 CC/day).

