12.5.1 Primary Analyses

12.5.1.1 COHb in blood and urinary concentrations adjusted for creatinine of MHBMA, 3-HPMA and S-PMA in 24 hour collection

COHb in blood and urinary concentrations adjusted for creatinine of MHBMA, 3-HPMA and S-PMA will be summarized as detailed in Section 12.1.3 “Descriptive Statistics”. In addition, the quantity excreted over 24 hours for each biomarkers of exposure will be presented.

The baseline is as defined in Section 12.1.4 “Definitions for Statistical Data Analysis”,

The values and percent changes from baseline in the concentration adjusted for creatinine will be listed and summarized along with the COHb concentrations and percent changes from baseline. In addition line graphs will be produced for means (and 95% CI) over all timepoints.

The transformed data will be analyzed by means of a generalized linear model using product arm as covariate adjusting for the following stratification parameters: sex and average cigarette consumption over the previous 6 weeks prior to Admission, and log-transformed baseline value of endpoint.

Assumptions of the analysis of variance model will be tested. Markedly non-lognormally distributed BoExp data will be transformed or analyzed by appropriate non-parametric methods.

The SAS code to be used is shown below:

```
Proc mixed data=_data_ ;  
Class product sex cigarette_cons ;  
Model log (Day 5) = log (baseline) sex cigarette_cons product ;  
Lsmean product / pdiff =control('CC') alpha=0.05 cl ;  
Run ;
```

The least squares (LS) means and estimate of the difference along with it's 95% CI will be back-transformed before presenting in the tables. The geometric LS means for each product along with the reduction (i.e: 100% - ratio of CHTP : CC) and 95% CI will be presented in the tables.

In addition line graphs will be produced for product geometric means (and 95% CI) over all timepoints for COHb in blood and urinary concentrations adjusted for creatinine of MHBMA, 3-HPMA and S-PMA.

The data will be presented in the below outputs, the TFL number refers to the TFL number in the accompanying TFL shell document:

TFL number	Title
TABLES	
15.2.3.1	Analysis of Biomarkers of Exposure for the Primary Objectives – FAS
15.2.3.2	Analysis of Urinary Quantity Excreted of MHBMA, 3-HPMA and S-PMA over 24 hours on Day 5 – FAS
15.2.3.3	Descriptive Statistics of Blood COHb (%) – FAS
15.2.3.3.1	Descriptive Statistics of Blood COHb (%) by Sex – FAS

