12.5.2.3 CYP1A2 Activity

CYP1A2 activity will be measured in plasma on Day -1 and Day 5. In this study the CYP1A2 activity will be calculated using the molar ratio of PX and CAF, as described in Section 7.1.3 “**CYP1A2**”. Descriptive statistics of the values and percent change on Day 5 from Day -1 and supportive listings will be provided.

The analysis will compare the Day 5 values between the CHTP and CC arms. An ANCOVA model will be used with terms for sex, average daily CC consumption over the last 6 weeks as reported during screening and product. The SAS code will be the same as described in Section 12.5.1.1 “**COHb in blood and urinary concentrations adjusted for creatinine of MHBMA, 3-HPMA and S-PMA in 24 hour collection**”.

LS means for each product along with the difference (CHTP - CC) and 95% CI will be presented in the tables.

The data will be presented in the below outputs, the TFL number refers to the TFL number in the accompanying TFL shell document:

TFL number	Title
TABLES	
15.2.4.26	Descriptive Statistics of CYP1A2 Activity (%) – FAS
15.2.4.27	Analysis of CYP1A2 Activity (%) on Day 5 – FAS
LISTINGS	
15.3.4.1	Listing of CYP1A2 Activity and Changes from Baseline

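### The smoking-intensity factor has conflicting definitions, and eight secondary or exploratory models as written can adjust for a category other than the randomisation stratum

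*SAP*

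**What the plan says.** **Randomisation.** Protocol 6.4: "Stratified randomization will be conducted by sex and by average daily CC consumption over the last 6 weeks prior to Admission as self-reported", cut at 10-19 and >19 CC/day. SAP 6.3.1 says the same. Protocol 12.1.1 and SAP 12.1.1 add the visit for the primary endpoints: "Average daily CC consumption over the 6 weeks prior to admission as reported on the Admission Day".

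**Protocol model.** Section 12.4.4 adjusts for "gender, average cigarette consumption over the previous 4 weeks, and baseline value of endpoint". The synopsis has "average cigarette consumption over the previous 4 weeks (value at admission for stratification", a 4-week window attached to a stratification value that is elsewhere a 6-week value.

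**SAP variable definition.** Table 10 in section 7.4, introduced as the list of categorical variables used in the study, gives the 10-19 / >19 split as "Daily CC consumption over the last 4 weeks as reported at Screening (per day".

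**SAP models.** Section 12.5.1.1 (primary) adjusts for "sex and average cigarette consumption over the previous 6 weeks prior to Admission, and log-transformed baseline value of endpoint". Exhaled CO (12.5.2.1.1) uses the same window, and the Day 5 urinary biomarkers (12.5.2.1.2) reuse the primary model. Eight other models take the Screening report. CYP1A2, for example, lists "average daily CC consumption over the last 6 weeks as reported during screening and product".

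**Data collected.** Protocol 7.3.3 asks "On average, how many cigarettes per day have you smoked over the last 6 weeks", and separately about average consumption since the subject started smoking. Appendix A schedules these questions at both Screening and Admission.

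**The concern.** A stratification factor that is also a model covariate needs one definition, fixed before database lock. Here one class variable, `cigarette_cons`, is given a recall window of 4 or 6 weeks and a reporting visit of Screening or Admission, depending on the section. A programmer following the text would adjust eight models for a category that need not be the one used to balance the arms. A programmer following Table 10 would look for a 4-week value that neither document describes collecting. At stake are agreement across models, the precision that comes from adjusting for the randomised factor, and a traceable record of departures from the protocol's confirmatory model.

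**Working it through.** **1. Definitions side by side**

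| Place | Window | Report |
|---|---|---|
| Protocol 6.4, SAP 6.3.1 (randomisation) | 6 weeks before Admission | visit not named |
| Protocol 12.1.1, SAP 12.1.1 | 6 weeks before Admission | Admission Day |
| SAP 12.5.1.1 primary; 12.5.2.1.1 exhaled CO; 12.5.2.1.2 Day 5 urinary | 6 weeks before Admission | visit not named |
| Protocol synopsis | 4 weeks | Admission |
| Protocol 12.4.4 | 4 weeks | visit not named |
| SAP Table 10 | 4 weeks | Screening |
| SAP 12.5.2.1.2 NEQ over time; 12.5.2.2 nicotine/cotinine; 12.5.2.3 CYP1A2; 12.5.3.1.1 QSU-brief; 12.5.3.1.2 MCEQ; 12.5.3.1.3 MNWS; 12.5.3.2 HPT; 12.5.3.4 CYP2A6 | 6 weeks | Screening |

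The last row is eight models: three secondary and five exploratory.

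**2. Text against code.** CYP1A2, HPT and CYP2A6 name the Screening report but take their SAS code from 12.5.1.1, where `cigarette_cons` stands for the 6 weeks before Admission. One variable name therefore carries two meanings. Table 18 labels the strata without a window or visit, so it does not settle the matter.

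**3. Can the two reports differ?** Protocol 9.1 places Screening 1 to 42 days before Admission. With a gap of g days, the 42-day window recalled at Screening shares 42 − g days with the 42 days before Admission:

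- g = 1: 41 of 42 days
- g = 14: 28 of 42
- g = 28: 14 of 42
- g = 42: 0 of 42

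At the longest gap the windows do not overlap at all. A subject whose answers fall on either side of 19/20 CC/day would enter these models in a category other than the stratum. The documents give no rate for this.

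**4. Record of changes.** SAP section 9 lists departures from the protocol down to a grammatical correction about creatinine adjustment. It does not list the move from 4 to 6 weeks.

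**5. Plausible effect, on assumed inputs only.** Residual log-scale SD from the plan's COHb CV: √ln(1 + 0.32²) = 0.31. Assumed: 80 subjects, 1:1 within sex-by-consumption strata of equal size; a stratum effect of 0.2 or 0.4 log units; 5% to 20% of subjects recorded in the other category; no treatment effect. Each data set was fitted with arm, sex and the recorded category. Over 100,000 simulated trials per setting:

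| Stratum effect | In other category | SE of arm effect, relative to correct category | One-sided type I error (nominal 2.5%) |
|---|---|---|---|
| 0.2 | 5% | 1.01 | 2.5% |
| 0.2 | 20% | 1.04 | 2.3% |
| 0.4 | 5% | 1.04 | 2.3% |
| 0.4 | 20% | 1.13 | 1.8% |

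Under these assumptions the standard error rises by about 1% to 13%, and the test keeps its level or becomes conservative. The model has no baseline covariate. Most of the eight models include one, which would probably absorb part of the stratum effect and shrink the loss.

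**The case against.** The best defence is that the analysis that matters is already right. SAP 12.5.1.1 names the stratification parameters and the 6-week window, SAP 12.1.1 fixes the Admission Day report for the primary endpoints, and protocol 12.1.1 agrees. Read with these, the protocol's 4 weeks is a slip, and the protocol leaves full details to the SAP. The eight affected models are secondary or exploratory, and none is multiplicity-controlled. All of that stands, and it limits the point. It does not remove it, because the eight sections and Table 10 still say something different.

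It may also be said that the phrase about screening means the whole Screening Period, which runs up to Admission. That does not help: Appendix A ends the screening column at Day -4 and lists Admission (Day -3) separately, so the Admission report falls outside it.

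A reader might infer more than the documents support:

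- *That every model using `cigarette_cons` is affected, including the primary one.* As worded in the SAP, the primary, exhaled CO and Day 5 urinary models match the stratum.
- *That stratified tables will disagree with the models.* Tables by consumption are planned only for the primary biomarkers and for demographics and baseline characteristics. SAP 12.1.1 and 12.3.2 define consumption for these over 6 weeks at Admission. The eight sections list no such tables.
- *That a 4-week value was never collected.* Protocol 7.3.3 lists no such question, but the eCRF on which the SAP draws is not available here.
- *That type I error is inflated.* Both reports precede randomisation, and the calculation shows no inflation.

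**Conclusion.** The inconsistency is real and should be corrected, but its reach is limited. The SAP's confirmatory analysis uses the right factor unless `cigarette_cons` is built from Table 10. The eight lower-tier models, followed as written, can adjust for a category that differs from the randomisation stratum in subjects whose Screening and Admission answers fall in different categories. The likely result is inconsistent adjustment and some loss of precision. How much cannot be derived from the documents, because they give neither the proportion of discordant answers nor the effect of the stratum on these endpoints; the 1% to 13% range illustrates assumed values only. Taking the Admission report as the randomisation value rests on protocol 12.1.1 and the synopsis, since protocol 6.4 names the window but not the visit.

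**What to change.** - In SAP 7.4, define `cigarette_cons` once as the randomisation stratum: 10-19 or >19 CC/day over the 6 weeks before Admission, as reported at Admission. Correct Table 10 to match.
- Replace the reference to the Screening report with that definition in SAP 12.5.2.1.2 (NEQ over time), 12.5.2.2, 12.5.2.3, 12.5.3.1.1, 12.5.3.1.2, 12.5.3.1.3, 12.5.3.2 and 12.5.3.4.
- State which value is used if the IxRS stratum and the Admission value on the CRF differ.
- Record in SAP section 9 that the 4-week covariate of the synopsis and protocol 12.4.4 is replaced by the 6-week stratum.

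The cost is SAP wording before database lock. The stratum is already held from randomisation and no new data are needed.

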8 SAMPLE SIZE JUSTIFICATION

The following discussion addresses the ability to detect a reduction of 50% or more in the levels of MHBMA, 3-HPMA, S-PMA, and COHb in CHTP 1.0 arm compared to the CC arm after 5 days of exposure, with 80 randomized subjects in a 1:1 ratio (40 in CHTP 1.0 arm and 40 in CC arm) and a one sided test with 2.5% type I error probability.

Table 11 describes the expected coefficients of variation (CV) and mean ratios (MR) between CHTP 1.0 and the control arm based on data from a controlled, randomized, open-label, 3-arm parallel single-center confinement study that investigated exposure to selected smoke constituents in smokers switching from CC to smoking article cigarettes for 5 days, the YVD-CS01-EU study (ClinicalTrials.gov: ID: NCT00812279) sponsored by PMI.

Table 11: Coefficients of Variation (YVD-CS01-EU study)	
	CHTP 1.0/CC
	MR (CV)
COHb	0.40 (0.32)
3-HPMA	0.30 (0.50)
MHBMA	0.15 (0.70)
S-PMA	0.20 (0.70)

Abbreviations: 3-HPMA = 3-hydroxypropylmercapturic acid; CC = Conventional cigarettes; COHb = Carboxyhemoglobin; CV = Coefficients of variation; MHBMA = Monohydroxybutenyl mercaptyuric acid; MR = Mean ratios; S-PMA = S-phenylmercapturic acid; CHTP 1.0 = Carbon Heated Tobacco Product 1.0

The power to detect a reduction was computed.

Table 12 describes the expected power to detect a reduction of 50% or more in the levels of MHBMA, 3-HPMA, S-PMA, and COHb in CHTP 1.0 arm compared to the CC arm after 5 days of exposure, with a one sided test with 2.5% type I error probability using the assumptions from YVD-CS01-EU.

Table 12: Expected Power (YVD-CS01-EU Studies Assumptions)						
	Reduction					
Assumptions	50%	51%	52%	53%	54%	55%
YVD-CS01-EU	88%	82%	73%	62%	49%	35%

The test-wise powers to detect a reduction of 50% or more in CHTP 1.0 arm compared to the CC arm after 5 days of exposure using the assumptions from YVD-CS01-EU are described in **Table 13**.

**Table 13: Test-Wise Power (YVD-CS01-EU study assumptions)**

Parameter	Test-wise power
COHb	88%
3-HPMA	>99%
MHBMA	>99%
S-PMA	>99%

Given the above calculation, the sample size was considered sufficient to have more than 80% power to detect a reduction of 50% or more in the levels of MHBMA, 3-HPMA, S-PMA, and COHb in CHTP 1.0 arm compared to the CC arm.

9 CHANGES FROM THE PROTOCOL SPECIFIED STATISTICAL ANALYSIS

Shift tables for safety endpoints will not be produced for this study. The relevant information provided in the listings is considered to be sufficient. Reason for change: the duration of the study would not allow for seeing trends in shifts tables.

Statistical analysis for the QSU-brief questionnaire data, MNWS questionnaire data and the MCEQ questionnaire data will be performed including interaction terms for product and time point to enable least square means to be calculated at each time point in order to explore the pattern of the CHTP 1.0 effect over time. The main comparison between products will be the comparison over all of the time points. Reason for change: this analysis would capture the daily evolution of perception of the product and the adaptation process taking into account the subjects' repeated measurements.

The second exploratory objective ("To evaluate the relationship between the levels of BoExp in 24-hour urine on Day 5 and NEQ in smokers switching from CC to CHTP 1.0, and in smokers continuing smoking CC") will be reported in a separate report. Reason for change: this analysis would be supportive only of analyses not accounting for NEQ difference between exposure groups.

A sensitivity analysis using the PP Population will be performed for every non-safety objective. This will be done if the FAS is not equal to the PP Population. If this is the case, then the table numbering as presented below will be adapted so that a ".1" is added to the FAS table and a ".2" is added to the PP table. Reason for change: the analysis on PP population would allow interpretability with studies in which PP population would be the primary set for analysis. The protocol was planning this analysis to be carried out only if

the PP population would differ from the FAS by more than 20%. It was decided to present the analyses for both FAS and PP regardless of difference in size between the two populations. .

The term “adjusted to creatinine” has been replaced by “adjusted for creatinine” in all relevant endpoints and analyses. Reason for change: the term was considered more grammatically correct than the original one from the protocol.

The descriptive statistics of the biomarkers of the primary endpoints will also be calculated per stratification factor. Reason for change: the protocol specified that primary endpoint analyses would be done by stratification factor, and this clarifies that descriptive statistics will also be presented by stratification factor.

An analysis of plasma nicotine and cotinine and NEQ will be done covering the exposure period. Reason for change: this analysis would serve to supplement the measure of difference of exposure between CC and CHTP arms over the entire exposure period.

New parameters were added to Human Puffing Topography Assessment (Number of peak(s) in the puff, Average puff volume per peak, Average puff duration per peak) in Tables 8 and 9. Reason for change: These additional parameters would improve the assesment of topography.

